# 4.3.8.2 Derivations

TTR (months) = (date of first confirmed objective response – date of first dose + 1) / (365.25/12).

# 4.3.8.3 Handling of Dropouts and Missing Data

Subjects without confirmed objective response, are treated as missing for the calculation of TTR. Only subjects who have achieved confirmed objective response (CR or PR) are evaluated for TTR.

# 4.3.8.4 Primary Analysis of Secondary Endpoint

The TTR is summarised (i.e., number of subjects [%] based on the number of responders) by the scheduled assessment timepoint that the response was first observed. The number of subjects with response at different disease assessment timepoints is provided. Additionally, descriptive summary statistics are presented.

The median TTR and two-sided 95% CI is assessed using the Kaplan-Meier method (without censoring because all subjects have events).

# 4.3.8.5 Supplementary Analyses of the Secondary Endpoint

Not applicable

# 4.3.9 Secondary Endpoint: Percentage Change in target lesion tumour size

Percentage Change in target lesion tumour size is a secondary efficacy endpoint.

# 4.3.9.1 Definition

An outcome endpoint for this study is percentage change from baseline in TL tumour size. This is based on RECIST TL measurements taken at baseline and each post-baseline assessment. Tumour size is the sum of the longest diameters (or short axis measurements for lymph nodes) of the TLs. Baseline for RECIST is defined to be the last evaluable assessment prior to first dose.

The TL tumour size and percentage change from baseline in the sum of TL tumour size at each assessment are calculated.

# 4.3.9.2 Derivations

Whenever TL tumour size data for the week 20 visit (note: or visit at which progression was documented if before week 20) is available then this is used in the analysis. A windowing rule is applied and follows the protocol allowed visit window, therefore RECIST scan performed within  $\pm 1$  week of the protocol scheduled visit is used for that visit. Subjects who progress before week 20 (plus 1 week allowing for a late assessment within the visit window) should have had a tumour assessment performed at the time of progression prior to study treatment discontinuation. The TL tumour size from their latest progression assessment is used instead of the week 20 assessment for these subjects.

The percentage change from baseline in TL tumour size is obtained for each subject by taking the difference between the sum of the TLs at week 20 (or earlier if the patient progressed) and the sum of the target lesions at baseline divided by the sum of the TLs at baseline times 100 (i.e. [week 20 – baseline] / baseline  $\times$  100).

#### 4.3.9.3 Primary Analysis of Secondary Endpoint

The TL tumour size and percentage change in TL tumour size from baseline is summarised using descriptive statistics and presented at each timepoint for the Safety set. Descriptive statistics for the percentage change from baseline at week 20 are presented, together with the number of subjects with a baseline and at least 1 post-baseline assessment.

The percentage change from baseline in TL tumour size is presented graphically using waterfall plots, with the bars ordered from the largest increase to the largest decrease. Separate waterfall plots are used to present each subject's week 20 percentage change in TL tumour size as a separate bar. A reference line at the -30% change in TL tumour size level is added to the plots, which corresponds with the definition of 'partial response'. All progressions are marked with a '•' or designated with patterns or colours for ORR categories. Flagged progressions on the percentage change in TL tumour size at week 20 are based upon NTL or new lesion progression at that timepoint and flagged progressions on the best percentage change are based upon NTL or new lesion progression at the same timepoint as the best percentage change. The scale in these plots is fixed to be from -100 to 100 to avoid presenting extreme values. Values that are capped as a result of this restriction to the scale are marked with '#'. Values are ordered in descending order with the imputations due to death appearing first followed by a gap followed by all other subjects. These plots will be produced for the Safety Set.

Additionally, 'spider' plots of percentage change from baseline in target lesion size by subject are presented. This depicts each subject's percentage change from baseline in TL tumour size as a line over time and progression due to non- target and/or new lesions are indicated. These plots will be produced for the Safety Set.

# 4.3.9.4 Supplementary Analyses of the Secondary Endpoint

Not applicable.

# 4.3.10 Secondary Endpoint: Best Percentage Change in target lesion tumour size

Best Percentage Change in target lesion tumour size is a secondary efficacy endpoint.

# 4.3.10.1 Definition

The TL tumour size and percentage change from baseline in the sum of TL tumour size at each assessment are calculated. The best absolute change in TL tumour size from baseline (i.e. depth of response) is the largest decrease from baseline or the smallest increase from baseline in the absence of reduction and includes all assessments:

- up to and including the first visit at which the overall visit response is PD,
- prior to death in the absence of progression,
- prior to the start of subsequent anti-cancer therapy (excluding radiotherapy);
- or up to and including the last evaluable RECIST assessment if the subject has not died, progressed or started subsequent anti-cancer therapy.

Each post-baseline disease assessment for a subject that meets the following conditions are included: all target lesions identified at baseline have measurements recorded at the current visit (i.e. they cannot be not done or not evaluable). If a lesion is recorded as  $\leq 5$  mm then this will be used in the calculations.

# 4.3.10.2 Derivations

If best percentage change cannot be calculated due to missing data (including if the patient has no TLs at baseline), a value of +20% will be imputed as the best percentage change from baseline in the following situations (otherwise best percentage change is left as missing):

- If a patient has no post-baseline assessment and has died
- If a patient has new lesions or progression of NTLs or TLs
- If a patient has withdrawn due to PD and has no evaluable TL data before or at PD

# 4.3.10.3 Handling of Dropouts and Missing Data

If best percentage change cannot be calculated due to missing data (including if the subject has no TLs at baseline), a value of +20% is imputed as the best percentage change from baseline in the following situations (otherwise best percentage change is left as missing):

• If a subject has no post-baseline assessment and has died
- If a subject has new lesions or progression of non-target lesions (NTLs) or TLs
- If a subject has withdrawn due to PD and has no evaluable TL data before or at PD

## 4.3.10.4 Primary Analysis of Secondary Endpoint

Descriptive statistics for the best percentage change from baseline are presented, together with the number of subjects with a baseline and at least 1 post-baseline assessment.

The best percentage change from baseline in TL tumour size is presented graphically using waterfall plots, with the bars ordered from the largest increase to the largest decrease. Separate waterfall plots are used to present each subject's best percentage change in TL tumour size as a separate bar. A reference line at the -30% change in TL tumour size level is added to the plots, which corresponds with the definition of 'partial response'. All progressions are marked with a '•' or designated with patterns or colours for ORR categories. Flagged progressions on the best percentage change in TL tumour size at week 20 are based upon NTL or new lesion progression at that timepoint and flagged progressions on the best percentage change. The scale in these plots is fixed to be from -100 to 100 to avoid presenting extreme values. Values that are capped as a result of this restriction to the scale are marked with '#'. Values are ordered in descending order with the imputations due to death appearing first followed by a gap followed by all other subjects. These plots will be produced for the Safety set.

# 4.3.10.5 Supplementary Analyses of the Secondary Endpoint

Not applicable.

## 4.3.11 Secondary Endpoint: Progression Free Survival

PFS is a secondary efficacy endpoint.

## 4.3.11.1 Definition

PFS is defined as the time from first dose of Cycle 0 until the date of first documented disease progression as assessed by investigator or death (by any cause in the absence of disease progression), regardless of whether the subject withdraws from study therapy or receives another anti-cancer therapy prior to progression.

## 4.3.11.2 Derivations

PFS (months) = (date of PFS event (progression/death) or censoring – date of first dose + 1) / (365.25/12)

Subjects who have not progressed or died at the time of analysis are censored at the time of the latest date of assessment from their last evaluable disease assessment. However, if the

subject progresses or dies immediately after two or more consecutive missed visits, the subject is censored at the time of the latest evaluable disease assessment prior to the two missed visits. (Note: a not evaluable visit is not considered as a missed visit).

For the first time period starting at cycle 0, two or more consecutive missing visits result in  $\geq 13$  weeks (4 weeks + 8 weeks+ 1 week for late assessment = 13 weeks). For the time period where the 8-weekly schedule applies, two or more consecutive missing visits resulting in  $\geq 18$  weeks after the last evaluable post-baseline disease assessment, allowing for early and late visits (i.e. 2 x 8 weeks + 1 week for an early assessment + 1 week for a late assessment = 18 weeks). The first interval in the 8-weekly schedule cycle 1 day 1 allows for 3 days early assessment despite 7 days for the interval that follow resulting in 122 days compared to 126 days for the later intervals.

If the two missed visits occur over the period when the scheduled frequency of RECIST assessments changes from 8-weekly to 12-weekly this equates to 22 weeks (i.e. the average of 8 and 12 weeks which gives 10 weeks and then apply the same rationale, hence  $2 \times 10$  weeks + 1 week for early assessment + 1 week for late assessment = 22 weeks).

When the scheduling changes to 12-weekly assessments, two missing visits equate to 26 weeks (2 x 12 weeks + 1 week for early assessment + 1 week for late assessment = 26 weeks).

In summary the two or more consecutive missed visits result in the following:

- If previous assessment is baseline: 4 weeks + 8 weeks+ 1 week (last assessment) ≥ 13 weeks (91 days),
- If cycle 1 day 1 scan was the previous evaluable visit: 8 weeks + 8 weeks + 3 days (visit window for cycle 1 day 1) + 1 week (3 days for early and 1 week for late assessment) ≥ 122 days,
- 3. If 8 week schedule applies but cycle 1 day 1 was not previous visit: 8 weeks + 8 weeks + 2 weeks (1 week for early and 1 week for late assessment)  $\geq$  18 weeks
- 4. If schedule changes from 8 weeks to 12 weeks: 8 weeks + 12 weeks + 2 weeks ≥ 22 weeks
- 5. During 12-weekly assessments: 12 weeks + 12 weeks + 2 weeks  $\ge$  26 weeks.

If subjects have no evaluable disease assessments post-baseline or do not have baseline tumour assessment data they will be censored at Day 1 unless they die within two visits of baseline (16 weeks plus 1 week allowing for a late assessment within the visit window) when the death date qualifies as a PFS event.

A summary of censoring rules and the date of PD/death or censoring are given in Table 8. Note that censoring overrides event in certain specified cases.

Situation	Date of PD/Death or Censoring	PFS Outcome
Documented PD or death in the absence of progression	Date of earliest documentation of PD or date of death in the absence of progression	Event
Either no tumour assessment at baseline or no evaluable assessments post-baseline AND death prior to second scheduled post-baseline disease assessment	Date of death	Event
Either no tumour assessment at baseline or no evaluable assessments post-baseline AND no death prior to second scheduled post-baseline disease assessment	Date of first dose	Censored
PD or death (in the absence of progression) immediately after $\geq 2$ consecutive missed disease assessments as per the protocol specified assessment schedule	Last evaluable progression-free disease assessment prior to missed assessments	Censored
On-going with neither PD nor death at the time of analysis or lost to follow-up or withdrawn consent	Date of last evaluable disease assessment	Censored

Fable 8	Summary of Censoring Rules for	or PFS
---------	--------------------------------	--------

PD = progressive disease; PFS = progression-free survival

The PFS time is always derived based on scan/assessment dates not visit dates.

RECIST assessments/scans contributing towards a particular visit may be performed on different dates. The following rules are applied:

- For investigator assessments, the date of progression is determined based on the earliest RECIST assessment/scan dates of the component that indicates progression.
- When censoring a subject for PFS the subject is censored at the latest of the dates contributing to a particular overall visit assessment.

Note: for TLs only the latest scan date is recorded out of all scans performed at that assessment for the TLs and similarly for NTLs only the latest scan date is recorded out of all scans performed at that assessment for the NTLs.

The proportion of subjects alive and progression-free at 3, 6, 9, 12 and 18 months from first dose is defined as the Kaplan-Meier estimate of PFS (per RECIST 1.1) at these specific months.

Potential duration of follow-up for PFS, applicable only for PFS censored subjects, is defined as follows:

Potential duration of follow-up for PFS in censored subjects (months) = (date of PFS censoring – date of first dose + 1) / (365.25/12).

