# 3.2.2 Study Treatment

During Cycle 0, patients will be treated with ceralasertib 240 mg BD, as oral tablets, from Days 1 to 7, Q28D, followed by an off-treatment period between Days 8 to 28 (i.e. no-dose period). From Cycle 1, patients will be treated with the combination of ceralasertib 240 mg BD, oral tablets, from Days 1 to 7, plus durvalumab 1500 mg Day 8, as an IV infusion, Q28D, until progressive disease (confirmed RECIST 1.1-defined radiological progression), unacceptable toxicity, withdrawal of consent, or if a study treatment discontinuation criterion is met.

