# 3.2.10 Derivations of RECIST 1.1 Visit Responses

For all subjects, the RECIST tumour response data is used to determine each subject's visit response according to RECIST version 1.1. It is also used to determine if and when a subject has progressed in accordance with RECIST and their best objective response to study treatment.

Baseline radiological tumour assessments should be performed no more than 21 days before the start of study treatment and ideally as close as possible to the start of study treatment. Tumour assessment is conducted every 8 weeks ( $\pm 1$  week) after the first dose (Cycle 1 Day 1) up to 18 months, then every 12 weeks ( $\pm 1$  week) until objective disease progression as per RECIST 1.1, irrespective of treatment decisions. Treatment start date will only be used to determine tumour assessment schedule, date of first dose will be used for analysis.

If an unscheduled assessment is performed, and the subject has not progressed, every attempt is made to perform the subsequent assessments at their scheduled visits. This schedule is followed in order to minimise any unintentional bias caused by some subjects being assessed at a different frequency than other subjects.

From the investigator's review of the imaging scans, the RECIST tumour response data is used to determine each subject's visit response according to RECIST version 1.1. At each visit, subjects are programmatically assigned a RECIST 1.1 visit response of CR, PR, SD or PD, using the information from TLs, NTLs and new lesions and depending on the status of

their disease compared with baseline and previous assessments. If a subject has had a tumour assessment that cannot be evaluated then the subject is assigned a visit response of NE, (unless there is evidence of progression in which case the response is assigned as PD).

Please refer to Table 5 for the definitions of CR, PR, SD and PD overall visit response.

RECIST outcomes (i.e. PFS, ORR etc.) are calculated programmatically for the site investigator data from the overall visit responses.

If there are patients with non-measurable disease or no evidence of disease assessed at baseline RECIST has been modified to allow the assessment of progression due to new lesions in subjects with no evidence of disease at baseline.

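### The sub-study PFS censoring rules rest on three scan schedules that do not agree, so the same early death is both an event and censored, and one missed scan may count as two

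*SAP*

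**What the plan says.** All references are to the biopsy sub-study SAP unless stated.

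- **Schedule (3.2.10).** "Tumour assessment is conducted every 8 weeks", with a window of 1 week either side, "after the first dose (Cycle 1 Day 1) up to 18 months, then every 12 weeks". No scan at Cycle 1 Day 1 is listed. "Baseline radiological tumour assessments should be performed no more than 21 days before the start of study treatment".
- **First missed-visit window (4.3.11.2).** "For the first time period starting at cycle 0, two or more consecutive missing visits result in" a gap of at least 13 weeks, built as 4 + 8 + 1. The numbered summary repeats this as 91 days when the previous assessment is baseline.
- **Second window (4.3.11.2).** "If cycle 1 day 1 scan was the previous evaluable visit", the limit is 122 days, which includes a 3-day early allowance given to that visit alone. The ordinary 8-weekly window is 18 weeks.
- **Death with no post-baseline scan (4.3.11.2).** Such a death is an event if it falls within two visits of baseline, put at 16 + 1 = 17 weeks.
- **Consequence (Table 8).** Progression or death straight after two or more missed assessments is censored at the last progression-free assessment before the gap.
- **Time origin (4.3.11.1).** "PFS is defined as the time from first dose of Cycle 0 until" progression or death.

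**The concern.** The two-missed-visits rule only makes sense relative to a scan schedule, and the sections imply different ones. The 13-week and 122-day limits presuppose a scan at Cycle 1 Day 1. Section 3.2.10 does not list it. The 17-week limit fits neither a schedule with that scan nor one counted in 8-week steps from Cycle 1 Day 1.

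For a subject whose last evaluable scan is baseline, censoring means leaving the risk set at time zero. An early progression or death handled this way drops out of the Kaplan-Meier curve altogether, which pushes the PFS estimates up. The programmer is also given two contradictory instructions for one group of deaths.

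**Working it through.** **Inputs.** Cycle 0 lasts 28 days (3.2.2: "followed by an off-treatment period between Days 8 to 28"), so without delay Cycle 1 Day 1 is 28 days after Cycle 0 Day 1. Scans are 56 days apart, ±7 days. The baseline scan is taken as 1 to 21 days before first dose. Days below are elapsed days after Cycle 0 Day 1, the PFS origin, unless stated.

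**1. The plan's own limits reproduce.**
- From baseline: (4 + 8 + 1) × 7 = 91.
- From the Cycle 1 Day 1 scan: (8 + 8) × 7 + 3 + 7 = 122.
- 8-weekly: (8 + 8 + 2) × 7 = 126.
- Death rule: (16 + 1) × 7 = 119.

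Each limit runs to the late edge of the second scheduled visit after the last evaluable one, plus any early allowance at the start. A limit of 91 puts that second visit at week 12, so the first must be at week 4, which is Cycle 1 Day 1. Likewise 122 = (28 + 112 + 7) − (28 − 3). A limit of 119 puts the second visit at week 16.

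**2. The schedules side by side.**

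| Schedule | Scans, weeks from Cycle 0 Day 1 | Late edge of second scan |
|---|---|---|
| Implied by the 91- and 122-day limits | 4, 12, 20 | 84 + 7 = 91 days (13 weeks) |
| 3.2.10, anchored at Cycle 1 Day 1 | 12, 20 | 28 + 112 + 7 = 147 days (21 weeks) |
| 3.2.10, first dose read as Cycle 0 Day 1 | 8, 16 | 112 + 7 = 119 days (17 weeks) |

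The 16-weeks-from-Cycle-1 rule for stable disease (4.3.6.2) and the week 20 tumour-size timepoint (4.3.9.2) fit scans at weeks 12 and 20. They do not settle whether there is a week 4 scan.

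**3. Death with a baseline scan and no post-baseline scan.** From day 91 to day 119 the gap is at least 13 weeks, so the subject is censored. Over the same days death is within 17 weeks, so it is an event. This conflict does not depend on which schedule is true.

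**4. One missed scan, if no Cycle 1 Day 1 scan is scheduled.**
- Anchored at Cycle 1 Day 1, the next scan falls on days 140 ± 7 = 133 to 147. All 15 in-window days are at least 91.
- Anchored at Cycle 0 Day 1, it falls on days 112 ± 7 = 105 to 119. Again all 15 are at least 91.

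Under either anchor, progression at that scan is censored at baseline after a single missed visit.

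**5. No missed scan, if no Cycle 1 Day 1 scan is scheduled.**
- Anchored at Cycle 1 Day 1, the first scan falls on days 84 ± 7 = 77 to 91. Counting from Cycle 0 Day 1, only day 91 meets the limit: 1 of 15.
- Counting from the baseline scan, gaps run from 77 + 1 = 78 to 91 + 21 = 112 days, and 224 of the 21 × 15 = 315 day combinations meet the limit. A scan exactly on time meets it when 84 + b ≥ 91, that is, when baseline was b = 7 to 21 days before first dose. These are counts of combinations, not probabilities.
- Anchored at Cycle 0 Day 1, the first scan falls on days 49 to 63, or 50 to 84 from the baseline scan. None meets the limit.

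**6. Size per subject (assumption: 30 analysed, the evaluable target in 3.2.1; no other early censoring).** If k subjects have had an event by a landmark, moving one to censored at time zero changes the event proportion from k/30 to (k − 1)/29, a fall of (30 − k)/870. For k = 1 that is 29/870 = 3.3 points; for k = 15 it is 15/870 = 1.7 points.

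**The case against.** The best defence is that a Cycle 1 Day 1 scan is in fact scheduled. Section 4.3.11.2 is written for the sub-study and gives that scan its own 3-day window, while the sentence in 3.2.10 closely follows the main-study SAP. Table 8 defers to the protocol's assessment schedule, which is not at hand. If the scan is scheduled, 91 and 122 days are the intended limits and the results in steps 4 and 5 do not apply. This stands: a reader might infer that the sub-study has no such scan, but the documents show only that 3.2.10 does not list one. The defence does not remove the conflict over deaths on days 91 to 119.

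Second, the governing idea is missed visits, and a subject scanned in window has missed none. The day 91 result is an edge effect of using at-least, and the 18-week window has the same edge. This is fair, but the SAP turns the rule into day limits, and a program that applies only those would censor such a subject.

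Third, the wording points to a count starting at Cycle 0, so the 224-of-315 figure rests on the less natural reading. That is right as far as it goes. The numbered summary speaks instead of baseline as the previous assessment, so the start needs stating.

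A reader might also infer that DoR inherits the problem. It does not. DoR includes only confirmed responders, who have at least two post-baseline response visits, so neither baseline nor a Cycle 1 Day 1 scan is their last evaluable assessment before the response ends.

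**Conclusion.** The point holds as an inconsistency within the sub-study SAP. Three scan schedules feed the PFS censoring rules, and as written a death on days 91 to 119 with a baseline scan but no later scan is both an event and censored.

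The rest is conditional on no Cycle 1 Day 1 scan being scheduled. Progression after a single missed first scan is then always censored at baseline. With no scan missed, progression at an in-window first scan is censored only on the last allowed day when the count starts at Cycle 0 Day 1, and only under the Cycle 1 Day 1 anchor. It is censored more often if the count starts at the baseline scan.

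Sub-study PFS could then be biased upward. That it would be is a stronger claim than the documents support: the schedule is unresolved and no missed-scan rate is given. The windows of 18, 22 and 26 weeks are not affected. PFS here is a secondary, descriptive, investigator-assessed endpoint in a single-arm sub-study, so the effect is on Kaplan-Meier estimates and not on a test. It is worth correcting because the rule gives contradictory instructions and the correction is cheap.

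**What to change.** Reconcile 3.2.10, the missed-visit windows in 4.3.11.2 and the two-visits-of-baseline death rule with the protocol's scan schedule. Then derive both the first missed-visit window and the death limit from that one schedule:

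- **Cycle 1 Day 1 scan scheduled:** list it in 3.2.10, keep the 122-day window, and use 4 + 8 + 1 = 13 weeks for both limits.
- **Not scheduled, scans anchored at Cycle 1 Day 1:** remove the 91-day and 122-day windows and use 4 + 8 + 8 + 1 = 21 weeks for both.
- **Not scheduled, scans anchored at Cycle 0 Day 1:** remove the same two windows and use 8 + 8 + 1 = 17 weeks for both.

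In every case, state that the first window counts from Cycle 0 Day 1 and that a subject scanned in window has not missed that visit. The cost is SAP wording and a few programming constants; no new data are needed.

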## 4.3.11.4 Primary Analysis of Secondary Endpoint

The analysis of PFS is based on the Full analysis set. The number and percentage of subjects experiencing a PFS event (broken down by type of event/censoring) are provided along with the median PFS and its two-sided 95% CI estimated using the Kaplan-Meier method. Kaplan-Meier plots of PFS are presented. Moreover, the landmark estimates of PFS at 3, 6, 9, and 12 months from first dose are summarised.

The treatment status at progression of subjects at the time of analysis are summarised. This includes the number (%) of subjects who were on treatment at the time of progression, the number (%) of subjects who discontinued study treatment prior to progression, the number (%) of subjects who have not progressed and were on treatment or discontinued treatment.

A summary of 'potential' duration of follow-up for PFS is included using median (range). This is presented for censored subjects (including all types of PFS censoring).

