## 4.3.12.4 Primary Analysis of Secondary Endpoint

The analysis of OS is based on the Full analysis set. The number and percentage of subjects experiencing an OS event and Kaplan-Meier plots of OS are presented. Additionally, summaries of the numbers and percentages of subjects who have died, those still in survival follow-up, those lost to follow-up and those who have withdrawn consent are provided. The median OS and two-sided *95*% CI are estimated using the Kaplan-Meier method.

Moreover, the landmark estimates of OS at 6, 9, 12, and 18 months from first dose are summarised with corresponding 95% CI.

A summary of the potential duration of follow-up for OS is included using median (range). This is presented for censored subjects.

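### Sub-study PFS: the 17-week limit for counting early deaths as events does not fit the sub-study scan schedule and contradicts Table 8 for subjects without an evaluable assessment

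*SAP*

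**What the plan says.** All references are to the biopsy sub-study SAP unless the main-study SAP is named.

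- **Time origin.** Section 4.3.11.1: "PFS is defined as the time from first dose of Cycle 0". Section 3.2.2 describes Cycle 0 as seven days of ceralasertib "followed by an off-treatment period between Days 8 to 28", so Cycle 1 Day 1 falls four weeks after first dose.
- **Missed-visit rule, section 4.3.11.2.** The list of limits opens with "If previous assessment is baseline: 4 weeks + 8 weeks+ 1 week (last assessment) ≥ 13 weeks (91 days". The next item begins "If cycle 1 day 1 scan was the previous evaluable visit" and gives 122 days. The section therefore treats the Cycle 1 Day 1 scan as the first post-baseline assessment and the scan eight weeks later as the second.
- **Rule for subjects with no evaluable post-baseline assessment or no baseline assessment, same section.** Their PFS time is cut off on Day 1, with one exception: "unless they die within two visits of baseline (16 weeks plus 1 week allowing for a late assessment within the visit window". A death inside that limit is a PFS event.
- **Table 8.** For the same subjects, death is an event only under the condition "AND death prior to second scheduled post-baseline disease assessment". Otherwise they are censored at the date of first dose.
- **Analysis sets.** Section 4.3.11.4: "The analysis of PFS is based on the Full analysis set". Section 4.3.12.4: "The analysis of OS is based on the Full analysis set". Table 6 defines only Enrolled, Safety, Pharmacokinetics and Pharmacodynamic sets, and lists PFS and OS under Safety.

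**The concern.** The text and Table 8 both describe a limit of two visits after baseline for the same group of subjects. The text translates it with the main-study schedule of scans at weeks 8 and 16. The sub-study has scans at weeks 4 and 12. The phrase matches section 4.3.9.2 of the main-study SAP word for word, whereas neighbouring sub-study rules were adapted: the tumour-size visit moved from week 16 to week 20, and the minimum duration of stable disease is counted from Cycle 1 Day 1.

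An early death in a subject with no usable scan can therefore be coded as an event on its own date or as censored at first dose, depending on which part of one section is programmed. If the choice is made once those deaths are known, it depends on the data. In a small single-arm cohort one reclassified subject is visible in the Kaplan-Meier estimate.

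**Working it through.** **Reproducing the plan's limits (days)**

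- Main study, two 8-weekly visits plus late window: (2 × 8 + 1) × 7 = 119. This agrees with the main-study SAP.
- Sub-study, two missed visits from baseline: (4 + 8 + 1) × 7 = 91. This agrees with section 4.3.11.2.
- Sub-study, previous scan at Cycle 1 Day 1: 56 + 56 + 3 + 7 = 122. This agrees.
- Sub-study, later limits: 18 × 7 = 126, 22 × 7 = 154 and 26 × 7 = 182. The stated sums in weeks agree.
- Sub-study death rule as written: (16 + 1) × 7 = 119. The sub-study's own two visits give 91. If the week-4 scan is ignored, because section 3.2.10 names only 8-weekly scans from Cycle 1 Day 1, two visits give (4 + 8 + 8 + 1) × 7 = 147. Neither reading gives 119.

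**Outcome for a subject with no evaluable post-baseline scan, by day of death**

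| Day of death | 17-week text | Table 8, week 12 without window | Table 8, week 12 plus 1 week | 91-day rule, if both scans were missed |
|---|---|---|---|---|
| 83 | event | event | event | does not apply |
| 84 to 90 | event | censored | event | does not apply |
| 91 to 119 | event | censored | censored | censored |
| 120 | censored | censored | censored | censored |

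The conflict spans 119 − 91 = 28 days. It starts 7 days earlier if Table 8 means the nominal week-12 date. If the scans were done but not evaluable, the last column does not apply, because a non-evaluable visit is not a missed one. Table 8 still conflicts with the text.

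**Effect of one such subject**

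Assume N = 30, no other censoring, and k other PFS events by the landmark. The 30 is the target number with at least two evaluable paired biopsies (section 3.2.1). It is not the size of the Safety set, which the document does not show.

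- 6 months, coded as event: S = 1 − (k + 1)/30 = (29 − k)/30.
- 6 months, censored at first dose: S = 1 − k/29 = (29 − k)/29.
- Difference: (29 − k)(1/29 − 1/30) = (29 − k)/870. For k = 0 this is 29/870 = 3.3 points; for k = 15 it is 14/870 = 1.6 points.
- 3 months is 3 × 365.25/12 = 91.3 days, so deaths on Days 91 to 119 lie essentially at or after this landmark. Coded as an event, the subject is still at risk: S = 1 − k/30. Censored at first dose: S = 1 − k/29. The difference is k/870, or 1.1 points at k = 10 and 1.7 at k = 15.

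**How many deaths could fall in the window**

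The document gives no figure. Assuming exponential survival with a median of 6 to 18 months, the share of all subjects dying between Days 91 and 119 is exp(−91λ) − exp(−119λ), with λ = ln 2/(median × 365.25/12). This is 7.1% at 6 months and 3.1% at 18 months. It is an upper bound for this issue, since only those without an evaluable post-baseline scan or without a baseline scan are affected.

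**The case against.** Five points can be made on the other side.

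- **Scope.** A reader might infer that every sub-study death in weeks 13 to 17 is coded two ways. The document does not support that. A subject with an evaluable week-4 scan who dies on Day 105 dies 105 − 28 = 77 days after it. That is inside the 122-day limit, so the death is an event with no conflict. This limit on scope stands.
- **Size.** A reader might also infer a shift of 1/30 at the 3-month landmark. That is wrong for deaths after Day 91.3, and at 6 months it is a maximum reached only when nobody else has had an event. This stands too. One exception is a death on Days 84 to 90 with Table 8 read without the window. It precedes the 3-month landmark, so (29 − k)/870 applies there.
- **Anchor.** The 16 weeks might have been meant from Cycle 1 Day 1, as for stable disease in section 4.3.6.2. The sentence says from baseline, however, and that reading gives 147 days from first dose, further from both Table 8 and the 91-day rule. The sponsor should confirm the anchor, but the contradiction does not go away.
- **Precedence.** Section 4.3.11.2 notes that censoring overrides an event in certain specified cases. This does not settle the matter, because the 17-week clause is itself the exception to censoring.
- **Analysis set.** A reader might infer that PFS and OS have no defined population. Table 6 assigns both to the Safety set. Both run from first dose, so an undosed subject has no time origin. The main-study full analysis set is all randomised subjects and cannot apply to a non-randomised cohort. The label in the text is a leftover with little or no numerical effect.

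**Conclusion.** The contradiction is real and confined to subjects with no evaluable post-baseline assessment or no baseline assessment. For them, a death on about Days 91 to 119 is a PFS event under the text of section 4.3.11.2 and censored at first dose under Table 8. The section's own calculation supports 13 weeks, and 17 weeks matches no pair of sub-study visits.

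The practical effect is small: up to 3.3 points on 6-month PFS per affected subject, possibly some movement in the median, and k/870 at 3 months. These figures assume 30 subjects and no other censoring, and a larger Safety set would make them smaller. PFS is descriptive here, the primary endpoint is CD8+ infiltration, and efficacy data are not pooled with the main study. The main-study rule is correct for its own schedule. The point should still be corrected, because it decides which deaths count as events. The analysis-set mismatch is a minor consistency correction.

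**What to change.** - In sub-study section 4.3.11.2, replace 16 weeks plus 1 week with 12 weeks plus 1 week, i.e. 13 weeks (91 days) from first dose of Cycle 0, after confirming that baseline is the intended anchor.
- In Table 8, state the same 13-week limit in both rows for these subjects and say that the late visit window is included.
- In sections 4.3.11.4 and 4.3.12.4, replace Full analysis set with Safety analysis set, as Table 6 already assigns.

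The cost is a handful of wording changes in the sub-study SAP, with no new data and no change to design or visits. They should be made before the sub-study PFS data are reviewed.
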